2.4 Safety evaluation

Safety evaluations including AE, SAE, laboratory, vital sign, confirmed blood pressure decreases, ECG etc. will be reported for safety population (SAF) by treatment as received.

2.4.1 Adverse events

2.4.1.1 AEs and SAEs

The incidence of AEs recorded through Day 5 and the incidence of SAEs recorded through Day 14 will be presented for the Safety population. Incident AEs will be considered those AEs with an onset date and time *after* the initiation of study drug. Adverse events with an onset between informed consent and study drug initiation will be listed separately. Adverse events will be coded using latest version of MedDRA. All reported AEs will be summarized by system organ class (SOC) and preferred term (PT) by treatment groups. Serious AEs (SAEs) will be summarized similarly. Percentages will be based on the number of subjects in the SAF.

In addition, SAEs will be summarized by time period of onset: from study drug initiation up to and including Day 5, or from Day 6 up to and including Day 14. All AEs through Day 14 will also be provided. After Day 14 only suspected serious adverse events will be collected and reported to Novartis. Additionally, a summary of AEs by PT and severity, using the worst reported severity grade for each event for the subject, will be provided. For analysis purposes, if the relationship to study drug is unknown or missing, the AE will be considered to be drug-related.

All study-drug-related AEs, AEs with an outcome of death, AEs leading to discontinuation of treatment, and study-drug-related SAEs, SAEs with an outcome of death, and SAEs leading to study drug discontinuation will be summarized by percentages and frequencies. For the analysis by time period of onset, the percentages will be based on the number of subjects at risk for AEs at the beginning of the period in the Safety Set. For each adverse event listed, the verbatim and coded terms, the corresponding severity, relationship to study drug, seriousness (yes/no), and start and stop date and time of the event will be specified and displayed by treatment group and subject number.

Detailed AE listings will also be provided.

2.4.2 Laboratory data

According to protocol, a central laboratory will be used for the analysis of all baseline and post-baseline specimens collected, except for hematology and clinical chemistry at screening, it will be done locally and the result will be entered into eCRF.

2.4.2.1 Hematology

The following hematology tests will be measured locally at screening and centrally at baseline and post-baseline: RBC, hemoglobin, hematocrit, platelet, and white blood cell count, including differentials.

2.4.2.2 Clinical chemistry

The following serum chemistry tests will be measured locally at screening and centrally at baseline and post-baseline: sodium, potassium, glucose, blood urea nitrogen (BUN) or urea, AST, ALT, alkaline phosphatase, total bilirubin, and creatinine. In addition, BNP/NT pro-BNP, eGFR and hemoglobinA1c will be measured locally at screening only.

Hematology and clinical chemistry data from central lab will be summarized for safety population by presenting shift tables using extended normal ranges (baseline to most extreme post-baseline value), summary statistics of raw data and change from baseline (means, medians, standard deviations, 1st and 3rd quartiles (Q1 and Q3), and by flagging of notable values in data listings. Shift tables are based on the cross-classification of the number of subjects with clinical laboratory values below (low), within (normal), or above (high) normal ranges for each laboratory test.

The number and percentage of subjects with clinically notable laboratory results after baseline will be presented. Clinically notable laboratory values are defined below.

Table 2-7 Clinically notable laboratory abnormalities for selected tests

Parameter	Criteria (based on a percent change from baseline)
Hematology	
RBC count	>50% increase, >25% decrease
Hemoglobin	>50% increase, >25% decrease
Hematocrit	>50% increase, >25% decrease
WBC count	>100% increase, >50% decrease
Platelet count	>100% increase, >50% decrease
Blood Chemistry	
ALT (SGPT)	defined in Section 2.4.7.1 (liver toxicity)
AST (SGOT)	defined in Section 2.4.7.1 (liver toxicity)
BUN	>100% increase
Creatinine	>100% increase
Total bilirubin (TBL)	defined in Section 2.4.7.1 (liver toxicity)
Alkaline phosphatase (ALP)	defined in Section 2.4.7.1 (liver toxicity)
Potassium	>25% increase, >25% decrease
Calcium	>20% increase, >20% decrease
Uric acid	>100% increase

ALT: alanine aminotransferase; AST: aspartate aminotransferase; ULN: upper limit of normal range

The data from local and central laboratory will be presented separately. All laboratory data from central lab will be listed for each subject. Laboratory values that are outside the normal ranges will be flagged high (H) or low (L). Data from local laboratory will be listed separately by lab.

Creatinine and eGFR

eGFR will be calculated using simplified Modification of Diet in Renal Disease (sMDRD).

The proportion of subjects with ≥ 0.3 mg/dL increase, ≥ 0.5 mg/dL increase, ≥ 1.0 mg/dL increase, and $>50\%$ increase from baseline in serum creatinine levels at each time point, and at any time point, will be presented.

The proportion of subjects with decreases from baseline eGFR of $>25\%$, $>40\%$, $>50\%$, and >30 mL/min/1.73 m² at each time point, and at any time point, will be presented.

In addition, worsening renal function based on serum creatinine and plasma cystatin-C values as one of efficacy variables is defined and discussed in [Section 2.2.3](#).

Blood sample for hepatitis serology

A blood sample will be collected at baseline and stored at the central laboratory for hepatitis serology analysis in case of a significant liver event (refer to [Section 2.4.7](#)).

2.4.3 Vital signs

For vital signs, descriptive statistics will be provided for values and change from baseline at each assessment time point for pulse, respiratory rate, body temperature, and weight. Treatment groups will be compared for changes from baseline using t-test.

Blood pressure and pulse during 48 hours drug infusion and 48 hours post infusion will also be listed.

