In the RELAX-AHF study, 1,161 AHF patients were randomized to receive either serelaxin (N=581) or matching placebo (N=580) on the background of standard of care AHF treatment. Serelaxin was administered according to a weight-range adjusted dosing regimen at the nominal dose of 30 µg/kg/day. The 48-hour intravenous infusion of serelaxin produced dyspnea relief as demonstrated by a 19.4% treatment improvement compared to placebo measured over 5 days by visual analogue scale (VAS), representing one of the two primary efficacy endpoints in the study. In addition, serelaxin treatment reduced signs and symptoms of congestion and significantly reduced WHF episodes through Day 5 and the overall length of index hospital stay, associated with a range of other in-hospital clinical benefits. Importantly, sustained benefits beyond the initial 48 hours of therapy were observed with serelaxin treatment, leading to a clinically and statistically significant 37% reduction in the risk of both CV and all-cause mortality through Day 180 ([Teerlink et al 2013](#)). These clinical improvements were associated with significant improvements in biomarkers consistent with reduction in end-organ damage in serelaxin treated patients ([Metra et al 2013](#)). With respect to safety, the adverse event profile after study drug exposure was generally comparable between serelaxin and placebo. Although more patients treated with serelaxin had blood pressure decreases, the decrease was manageable; the incidence of hypotension was comparable between serelaxin and placebo groups. Fewer patients in the serelaxin arm had an increase of serum creatinine > 0.5 mg/dL at Day 5 versus placebo (p=0.003). There were also fewer treatment emergent events associated with renal impairment, which may indicate preserved renal function. Overall, the data demonstrated that serelaxin was generally safe and well- tolerated.

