study drug must be permanently discontinued. Measures may be taken by the investigator to address the decrease in blood pressure during the intervening 15 minutes, if clinically indicated. Should the study drug dose be decreased or the study drug be discontinued prematurely due to blood pressure decrease, then measurements should be recorded every half hour through 2 hours following the blood pressure decrease event, and then hourly through 5 hours after event onset. Upon completion of the 5 hour post event onset time point, heart rate and blood pressure measurements should be resumed as outlined in [Section 6.5.2](#). If hypotension persists beyond the 5 hours post event onset, continued hourly blood pressure monitoring should be considered by the investigator, if clinically indicated. Additional blood pressure data collected beyond the 5 hours post event should be captured in the source documents; only heart rate and blood pressure outlined in [Section 6.5.2](#) will be entered into the eCRFs.

All randomized patients will be assessed daily up to and including Day 5, and then followed up at scheduled visits for a period of 180 days. They are required to receive standard of care treatment for HF during both the index hospitalization and post discharge per local and institutional practice guidelines. Visits to assess efficacy are scheduled on Days 5, 14 (telephone), 30 (telephone), 60, 120 and 180. All AEs will be collected up to and including Day 5 and all serious adverse events (SAEs) will be collected up to and including Day 14, regardless of suspected causality. After Day 14 only suspected SAEs will be collected and reported to Novartis.

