h A complete physical examination will be performed at screening; an abbreviated physical examination will be performed at all other specified time points. Refer to [Section 6.5.1](#)

i In addition to at screening and baseline, BP and HR (pulse) measurements are to be performed at 30 and 60 minutes and then every hour for the first 6 hours of study drug infusion, and then every 3 hours during study drug infusion, including night time hours. Post-infusion, BP and HR are to be measured every 3 hours until 12 hours following end of infusion, then every 6 hours for up to 48 hours and then every 24 hours until the earlier of Day 5 or Discharge. In addition BP and HR measurements will be taken at Day 60, and Day 180 as part of vital signs assessment. BP and HR are to be measured with the patient in the same position and with the same equipment using the same arm, throughout study drug infusion. These measurements may be made and recorded by trained healthcare personnel as part of their routine clinical duties, as well as study personnel. The assessments made as per the table above would be entered in the CRFs. Assessments at other time points will be part of source document. Refer to [Section 6.5.2](#)

j Blood will be locally collected at screening . Refer to [Section 6.5.3](#)

k Blood will be collected for measurement of biochemistry, hematology and samples shipped to the central laboratory for analysis. Refer to [Section 6.5.3](#).

m AEs will be collected from the signing of the ICF to and including Day 5. SAEs will be collected from the signing of the ICF to and including Day 14. After this period, only suspected SAEs will be collected.

lUrine dipstick will be measured locally at screening to rule out any conditions requiring further diagnostic evaluation or treatment. Refer to [Section 6.5.3.4.](#) .

n ECGs will be performed and interpreted locally at screening, at 48 hours, and at Day 5 or discharge, whichever occurs first. The ECG interpretation and person interpreting the ECG must be recorded in the source documents and in the eCRF Refer to [Section 6.5.4..](#)

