### **6.5 Safety**

Safety will be assessed by comparing the serelaxin group to the standard of care only group with regard to the frequency of adverse events (AEs)/ SAEs, changes in vital signs, physical examination findings, and clinical laboratory test results (chemistry and hematology). All AEs will be assessed up to and including Day 5 and SAEs will be assessed up to and including Day 14. Any SAEs experienced after Day 14 should only be reported to Novartis if the investigator suspects a causal relationship to study treatment.

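### No by-arm summary of blood pressure level or change in all treated patients is planned, and the protocol is unclear on which blood pressure readings enter the eCRF

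*SAP*

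**What the plan says.** **Analysis.** SAP 2.4.3 states that "descriptive statistics will be provided for values and change from baseline at each assessment time point for pulse, respiratory rate, body temperature, and weight". It continues: "Treatment groups will be compared for changes from baseline using t-test". Its only provision for BP is: "Blood pressure and pulse during 48 hours drug infusion and 48 hours post infusion will also be listed". Protocol 9.5.2 plans its summaries and t-tests in the same words, "for pulse, respiratory rate, body temperature, and weight". Neither passage shows a redaction or gap where BP might have stood.

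**Aim.** Protocol 6.5 says safety will be assessed by comparing the groups on, among other things, "changes in vital signs, physical examination findings, and clinical laboratory test results". Protocol 6.5.2 treats BP as a vital sign. Protocol 1.1 reports of the earlier phase III trial: "Although more patients treated with serelaxin had blood pressure decreases". Protocol 3.6 attributes BP falls to the drug's vascular mechanism.

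**BP analyses that are planned.** SAP 2.4.5 gives the number and proportion of patients with a confirmed BP decrease during infusion. It characterises those events and shows the BP course after the first one, up to Day 5. SAP 2.4 reports this by treatment received. SAP 2.4.1.2 and Table 2-6 report hypotension adverse events by arm with an odds ratio and 95% CI.

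**Data capture.** Protocol 6.5.2 sets a dense BP schedule. Footnote i to Table 6-1 repeats it, sends the table's time points to the CRF, and says of the rest: "Assessments at other time points will be part of source document". Protocol 3.1, after describing extra monitoring following a BP-decrease event, says that "only heart rate and blood pressure outlined in" Section 6.5.2 will go into the eCRFs.

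**The concern.** The protocol describes the drug as BP-lowering and builds dose-adjustment rules on systolic BP, yet BP is missing from the table that would show the size and time course of that effect across all treated patients. As written, the study report would contain a between-arm t-test of body temperature but no mean difference in systolic BP at any time point. A reader who wanted to know how far and for how long BP was shifted, including in patients who never met an event threshold, would have only individual listings.

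The data-capture question bears on the same output. If only the Table 6-1 readings are entered, the SAP listing covering 48 hours of infusion and 48 hours afterwards would rest on a small part of the readings taken at the bedside.

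**Working it through.** The plan states no figure on this point, so there is none to reproduce. The check is a comparison of texts, a count of readings and a precision calculation.

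**1. What each planned BP output covers**

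| Output | By arm? | Patients covered | BP level or change over time? |
|---|---|---|---|
| SAP 2.4.3 / protocol 9.5.2 summaries and t-tests | Yes | All treated | Not for BP |
| SAP 2.4.3 BP listing | No comparison | All treated | Individual values only |
| SAP 2.4.5 event proportions | Yes | All treated, during infusion | No |
| SAP 2.4.5 event magnitude, trough and later course | Yes | Only patients with a confirmed decrease | Yes, from the event on |
| SAP Table 2-6 hypotension adverse events | Yes | All treated | No |

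No row is by arm, in all treated patients, and on BP level or change.

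**2. What an event count can miss.** SAP 2.4.5 gives no threshold of its own but ties confirmed decreases to dose reduction or discontinuation. I therefore read it with protocol Table 5-2: a fall of more than 40 mmHg with systolic BP still at or above 100, or systolic BP below 100.
- Baseline 140 mmHg, falling to 100: the change is 40, which is not more than 40, and 100 is not below 100. No event.
- Baseline 125 mmHg (the entry minimum), falling to 100: the change is 25. No event.

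A shift across many patients within these limits would not appear in the event proportions. Nor would any BP difference after the infusion ends, because confirmed events are counted only during administration.

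**3. Scheduled readings from infusion start to 48 hours post-infusion (protocol 6.5.2)**
- Infusion: 0.5, 1, 2, 3, 4, 5 and 6 h = 7; then every 3 h from 9 to 48 h = 14. Total 21.
- Post-infusion: every 3 h to 12 h (51, 54, 57, 60) = 4; then every 6 h up to 48 h (66, 72, 78, 84, 90, 96) = 6. Total 10.
- All: 21 + 10 = 31.
- On Table 6-1 time points: 6, 12, 24, 48, 72 and 96 h = 6.
- Source only under footnote i: 31 − 6 = 25, of which 21 − 4 = 17 fall during infusion.

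The six-hourly phase could instead be read as running for 48 hours from hour 12 post-infusion. That adds readings only after 96 h and leaves 31 and 6 unchanged. The count assumes the patient is still in hospital and receives the full infusion.

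**4. Precision if BP is added.** Inputs: 1,520 randomized 1:1 (protocol 9.7), so 760 per arm. The SD is an assumption, because the documents give none. Half-width = 1.96 × SD × √(2/760) = 1.96 × SD × 0.0513.
- SD 15: 1.5 mmHg
- SD 20: 2.0 mmHg
- SD 25: 2.5 mmHg

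**The case against.** The strongest reply is that BP is far from neglected. Confirmed decreases are reported by arm with timing, magnitude, trough, outcome, treatment and an examination of the interaction with IV nitrates. Baseline characteristics and concomitant medications are tabulated for patients with and without an event. Hypotension adverse events have an odds ratio. All of this stands. A reader might infer from SAP 2.4.3 that no by-arm BP analysis is planned at all, and the documents do not support that: the gap is confined to BP level and change in all treated patients.

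Two further inferences should be resisted. The documents show that serelaxin lowers BP, but not that BP is the only vital sign it affects. They also do not rank hypotension as the main risk: SAP Table 2-6 lists it beside two other safety risks, and protocol 1.1 reports comparable hypotension incidence between arms in the earlier trial.

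On data capture, it can be said that the protocol 3.1 sentence concerns extra readings after a BP-decrease event and limits what is entered, while footnote i is the general rule. That has force, and a flat contradiction over the routine schedule is more than the text supports. But the sentence still names the Section 6.5.2 readings as the eCRF content, and Section 6.5.2 is the dense schedule, so the two places can be followed differently. Nor does it follow that footnote i would damage the confirmed-decrease analysis. Table 6-1 has a separate eCRF row for BP-decrease events, and event readings may be captured there.

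**Conclusion.** The point holds as a gap in safety reporting. Protocol 6.5 promises a comparison of vital-sign changes. SAP 2.4.3 and protocol 9.5.2 deliver it for four variables and leave BP out, and the event-based analyses do not replace it because they depend on thresholds, cover the infusion period or follow only patients who had an event. An all-patient estimate is readily available at about ±1.5 to ±2.5 mmHg per time point. This assumes an SD of 15 to 25 mmHg and close to 760 patients per arm with data; it would widen as readings are lost.

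The eCRF question is a wording conflict that needs clarifying. If footnote i governs, the planned listing would hold 6 of 31 scheduled readings, apart from any on the BP-decrease event form. If the reference in protocol 3.1 to Section 6.5.2 governs, it would hold all 31.

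Neither issue touches the primary endpoint, the type I error or the planned by-arm results for confirmed decreases and hypotension.

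**What to change.** - In SAP 2.4.3 and protocol 9.5.2, add systolic and diastolic BP to the by-arm descriptive statistics and the change-from-baseline comparison at the Table 6-1 time points, reporting the mean difference with 95% CI. The cost is a wording change and one extra table. These readings are in the eCRF under either reading of the capture rule, so the sites have no new work.
- Reconcile protocol 3.1 and Section 6.5.2 with Table 6-1 footnote i, so that one statement says which BP and heart-rate readings are entered, and align the SAP 2.4.3 listing with it. If the full Section 6.5.2 schedule is meant, the cost is data entry of readings already taken. If only the Table 6-1 time points are meant, the SAP should say that the listing is limited to those, plus any readings held on the BP-decrease event form.

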2.4.4 Electrocardiogram (ECG)

The following quantitative variables will be summarized: ventricular rate, PR interval, QRS duration, QT interval, and corrected QT interval (QTc).

The number and percentage of subjects with the following criterion will be presented.

- QT > 500 msec
- QT > 480 msec
- QT > 450 msec
- QT increases from baseline ≥ 30 msec
- QT increases from baseline ≥ 60 msec
- PR > 200 and ≤ 220 msec
- PR > 220 msec
- PR increases from baseline $> 25\%$ (PR > 200 msec)
- QRS > 110 and ≤ 120 msec
- QRS > 120 msec
- QRS changes from baseline $> 25\%$ (QRS > 110 msec)

- Heart rate >100 beats per minute
- Heart rate < 50 beats per minute

QT data will be analyzed for the Fridericia (primary) corrections.

In addition, shift tables comparing baseline ECG results (normal, abnormal, not available, total) with the maximum on-study result (normal, abnormal, not available, total) will be provided for each variable.

A listing of all newly occurring or worsening abnormalities will be provided, as well as a by-subject listing of all quantitative ECG parameters.

2.4.5 Confirmed blood pressure decreases

The number and proportion of subjects who experience a confirmed blood pressure decrease event during study drug administration will be provided. Among subjects who experience a confirmed blood pressure decrease event, the events will be further characterized with respect to impact on study drug administration (dose decreased or study drug discontinued), the timing of event onset relative to study drug initiation, the magnitude of the blood pressure decrease at its onset and the trough blood pressure recorded, the blood pressure measurements after study drug discontinuation, outcome, treatment(s) required, and whether considered symptomatic, i.e. an AE. Summaries will be provided separately for those confirmed events that resulted in study drug dose reduction, and those that resulted in study drug discontinuation. The possible interaction between the effect of serelaxin and the effect of IV nitrate administration within the first 48 hours will be examined.

Course of blood pressure after the occurrence of first CBPD up to Day 5 will be presented.

To further investigate the impact of CBPD, the following analyses will be performed.

- Baseline characteristics by CBPD subgroup (yes/no).
- Concomitant medications by CBPD subgroup (yes/no).
- AEs associated with the occurrence of the CBPD.

2.4.6 Pregnancy test results

Positive results will be presented in listing.

2.4.7 Liver toxicity function and liver events

Liver event and laboratory trigger definitions are defined in Appendix 2 of protocol.

2.4.7.1 Liver toxicity function

The liver toxicity (LFT abnormality) will be identified with the Adverse Event (jaundice and “Drug-related hepatic disorders - severe events only” SMQ AE), and the laboratory parameters mainly AST (aspartate aminotransferase; also known as SGOT), ALT (alanine aminotransferase; also known as SGPT), ALP (alkaline phosphatase) and TBL (total bilirubin; conjugated (direct) and unconjugated (indirect) bilirubin).

The standard SMQ-PT table and odds ratio will be used to provide the number and percentage of subjects with hepatic disorders as mentioned in [Section 2.4.1.2](#), Selected AEs.

The laboratory parameters for liver function will be shown in the laboratory standard tables as discussed in [Section 2.4.2.2](#).

In addition, summary tables will be provided on the number and percentage of subjects who meet the following criteria at post baseline.

Table 2-8 Criteria for evaluating liver toxicity

[figure not shown]
Parameter	Criterion
ALT or AST	ALT or AST > 3xULN ALT or AST > 5xULN ALT or AST > 8xULN ALT or AST > 10xULN
Hy's category	ALT or AST >3x ULN and TBL >1.5x ULN ALT or AST > 3xULN & TBL > 2xULN ALT or AST > 5xULN & TBL > 2xULN ALT or AST > 8xULN & TBL > 2xULN ALT or AST > 10xULN & TBL > 2xULN ALT or AST > 3xULN & TBL > 2xULN & ALP < 2xULN
TBL&ALP	TBL >1.5x ULN and ALP >2x ULN TBL >2x ULN and ALP >2x ULN
Isolated TBL	TBL >1.5x ULN & ALT and AST \leq 3x ULN and ALP \leq 2x ULN TBL >2x ULN & ALT and AST \leq 3x ULN and ALP \leq 2x ULN TBL >3x ULN & ALT/AST \leq 3x ULN and ALP \leq 2x ULN
Isolated ALP	ALP >1.5x ULN & ALT and AST \leq 3x ULN and TBL \leq 1.5x ULN ALP >2x ULN & ALT and AST \leq 3x ULN and TBL \leq 1.5x ULN ALP >3x ULN & ALT and AST \leq 3x ULN and TBL \leq 1.5x ULN ALP >5x ULN & ALT and AST \leq 3x ULN and TBL \leq 1.5x ULN

ALP: alkaline phosphatase; ALT: alanine aminotransferase; AST: aspartate aminotransferase; TBL: total bilirubin; ULN: upper limit of normal.

Plots showing the relationship between TBL and ALT or AST (eDish plot) will also be provided.

